#### 9.2.1. Dose Modifications for Non-hematologic Toxicity Unrelated to Selinexor

For all ≥ Grade 3 non-hematologic toxicitiles that are NOT selinexor related:

- Hold selinexor dose until AEs resolves to ≤ Grade 1 or baseline (maximum 28 days). Exceptions to this include: Patients with grade ≥3 nausea, vomiting or diarrhea can continue selinexor unless optimal supportive therapies have already been administered for at least 3 days days without improvement of the nausea, vomiting, or diarrhea. Optimal supportive therapies (see Supportive Care Guidelines, Section 9.1.3).
- If the AEs resolve to ≤ Grade 1 or baseline within 28 days, restart Selinexor at the same dose.
- If the AEs do not resolve to ≤ Grade 1 or baseline within 28 days of discontinuation of study drug, study drug will be discontinued permanently.

In exceptional situations, if the patient has experienced objective evidence of clinical benefit, and in the opinion of the investigator no safety concerns are present and it is in the best interest of the patient to remain on study, the patient may continue to receive study treatment after the 28-day delay. The rationale for continuing study treatment will be documented in the patient's medical record.

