#### 9.2.3. Dose Reductions for Renal Impairment

Because the impact of renal dysfunction on Selinexor is not known, patients with GFR <30mL/min are not eligible to enter the study. Refer to dose adjustment guidelines below for renal dysfunction that develops while on study and unrelated to Selinexor.

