#### Dose Adjustment Guideline for renal dysfunction while on study

Renal Dysfunction	Recommended Action
Normal to Moderate (GFR ≥ 30 mL/min)	Full dose
Severe (GFR < 30 mL/min)	
 
Reduce Selinexor by 30% for at least two weeks
 
If reduced dose is well tolerated, or GFR increases to >30mL/min, then Selinexor may be increased to starting dose after consultation with the Principal Investigator.
 

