#### 9.2.5. Conditions Not Requiring Selinexor Dose Reduction

The following conditions are exceptions to the above guidelines. Selinexor does not need to be held in the following cases:

- Grade 3 nausea, vomiting or diarrhea (unless persisting > 3 days with adequate treatment of anti-emetics or anti-diarrheals
- Alopecia of any grade
- Weight loss of less than 20%
- Electrolytes abnormalities that are reversible with oral supplements or brief intravenous infusions.

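### For renal dysfunction unrelated to selinexor with GFR below 30 mL/min and Grade 3 or higher, Sections 9.2.1 and 9.2.3 give incompatible dosing instructions, and no text says which governs

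*Combined protocol and SAP*

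**What the plan says.** Section 9.2.1 opens with a broad scope: "For all ≥ Grade 3 non-hematologic toxicitiles that are NOT selinexor related". For these events the instruction is "Hold selinexor dose until AEs resolves to ≤ Grade 1 or baseline (maximum 28 days". If the event resolves in that time, staff are to "restart Selinexor at the same dose"; if not, "study drug will be discontinued permanently". A closing paragraph lets a patient with objective benefit and no safety concern continue past 28 days in exceptional situations. The section also names some events that need not be held: "Exceptions to this include: Patients with grade ≥3 nausea, vomiting or diarrhea can continue selinexor", subject to a condition on supportive care.

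Section 9.2.3 excludes patients with GFR below 30 mL/min from entry, because the effect of renal dysfunction on selinexor is unknown. It then says: "Refer to dose adjustment guidelines below for renal dysfunction that develops while on study and unrelated to Selinexor". The table that follows has two rows. At GFR of 30 mL/min or more, full dose is given. Below 30, the row labelled severe, the recommended action is "Reduce Selinexor by 30% for at least two weeks". A return to the starting dose is allowed, after consultation with the Principal Investigator, if the reduced dose is well tolerated or GFR rises above 30. The table mentions no hold, no resolution grade, no time limit and no discontinuation.

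Neither section cites the other. Section 9.2.7 asks that all delays, modifications and reintroductions be made in consultation with the Principal Investigator.

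**The concern.** Both sections are limited to events not attributed to selinexor, so attribution does not separate them. One runs on CTCAE grade and the other on GFR, and nothing links the two scales. A patient whose renal event meets both triggers is off drug under one section and on reduced drug under the other, at a level of renal function where the protocol says the drug's behaviour is unknown.

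Three things depend on the choice: the drug the patient receives, whether treatment ends, and possibly whether the patient counts in the response evaluation cohort. Section 14 also plans toxicity proportions by the dose received when the toxicity occurred, so the choice affects how later events are classified.

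**Working it through.** There is no figure of the plan's own to reproduce. The check compares the texts and adds short arithmetic for the size of the gap.

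**Step 1. The two rules side by side, for an event unrelated to selinexor.**

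| | Section 9.2.1 | Section 9.2.3 |
|---|---|---|
| Trigger | Grade 3 or higher, non-hematologic | GFR below 30 mL/min, no lower bound |
| Action | Hold | Continue, reduced by 30% |
| Minimum or maximum time | At most 28 days held | At least two weeks reduced |
| Return | Same dose, on resolution to Grade 1 or lower or to baseline | Starting dose, if tolerated or GFR above 30 |
| Unresolved at 28 days | Permanent stop, with an exceptional-benefit override | Not addressed; dosing may go on |

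**Step 2. Do the triggers overlap?** Section 9.2.1 applies to every non-hematologic toxicity of Grade 3 or higher in this attribution class, and the lower row of the 9.2.3 table has no floor. Any renal event that is Grade 3 or higher with GFR below 30 therefore meets both. How much of that row is Grade 3 or higher cannot be read from the documents: CTCAE 4.03 is cited by link (Section 9.2 and the CTCAE appendix) and its renal grades are not reproduced.

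**Step 3. Exposure per cycle.** Inputs from Section 9.1.1: starting dose 60 mg, 4 doses per 21-day cycle.
- Full dose: 4 × 60 = 240 mg.
- Held for the whole cycle (9.2.1): 4 × 0 = 0 mg.
- Reduced by 30% (9.2.3): 60 × 0.70 = 42 mg per dose; 4 × 42 = 168 mg.

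The 168 mg is nominal. Table 1 has only 60 mg and 40 mg doses, and whole tablets of 10, 20 and 25 mg (Section 5.1) combine only to multiples of 5 mg, so 42 mg cannot be dispensed exactly.

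**Step 4. Discontinuation.** Beyond 28 days unresolved, 9.2.1 normally ends treatment; 9.2.3 does not. Section 13.0 adds a second route: a patient who misses 3 or more of 4 doses in a cycle without drug-related toxicity is discontinued. If held doses count as missed, which the protocol does not say, a hold for an unrelated event could trigger this within one cycle. Reduced dosing under 9.2.3 would miss none.

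**Step 5. Evaluability.** Section 14 requires at least 3 of the 4 planned first-cycle doses, plus a disease assessment. A cycle 1 hold that costs 2 doses leaves 4 − 2 = 2, which fails. Under 9.2.3 all 4 doses are given, though smaller.

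**The case against.** The best reply is that 9.2.1 is the general rule and 9.2.3 the specific one. Section 9.2.3 has its own trigger, action and recovery rule, and directs staff to it for unrelated renal dysfunction. Infection likewise has its own section, 9.2.4. On that view only a cross-reference is missing. The reading is plausible, but the protocol never states it, and it runs against the unrestricted scope of 9.2.1. Section 9.2.4 gives little help: it also withholds drug and resumes at the original dose, so it sits closer to 9.2.1 than the renal table does.

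Second, Section 9.2.7 brings the Principal Investigator into every modification, in a single-center trial of 20 patients. That reduces the risk of inconsistent handling. It does not settle in advance which rule applies.

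Several stronger inferences are tempting and should be resisted:
- A reader might infer that the sections conflict at every GFR below 30. The severe label in 9.2.3 is a GFR category, not a CTCAE grade, so the documents do not show this. Entry at a creatinine clearance of 30 mL/min shows that the GFR threshold can be crossed easily, not that Grade 3 is reached.
- A reader might take the absence of renal dysfunction from Section 9.2.5 as proof that no exception exists. That section says "The following conditions are exceptions to the above guidelines", but it lists conditions that need no dose reduction. A condition for which 9.2.3 recommends a reduction would not be expected there.
- A reader might treat the exceptions in 9.2.1 as a closed list. The wording introducing them is not exhaustive.
- A reader might say that 9.2.3 orders continued dosing. Its table gives a recommended action within a guideline.

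**Conclusion.** The point stands for renal dysfunction that is unrelated to selinexor, has GFR below 30 mL/min and is Grade 3 or higher. For such an event the plan gives two incompatible instructions and no order of precedence. The per-patient size is 0 mg against a nominal 168 mg in a full cycle, assuming a 60 mg dose and a hold lasting the whole cycle, together with a different outcome at 28 days. The evaluability effect applies only to a cycle 1 event, and the Section 13.0 effect only if held doses count as missed.

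The number of patients affected cannot be estimated from the documents. A reader might infer that the design's operating characteristics are at risk; they are not, since the Simon sample sizes, decision thresholds and error rates do not depend on this rule. The matter is consistency of safety management and of exposure and discontinuation records. It should be corrected because the two sections differ on whether to dose at a renal function that the protocol treats as unstudied.

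**What to change.** Reconcile Sections 9.2.1 and 9.2.3. State in both which one governs renal dysfunction that is unrelated to selinexor and Grade 3 or higher, and make the hold, restart and 28-day provisions agree. The restart wording needs the same attention, since one section returns to the same dose and the other to the starting dose. The clinical rule is for the investigators to choose; this review takes no view on it.

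The cost is a protocol amendment with about one cross-reference sentence in each section and the matching edits. No procedures, visits or patients are added.

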# 9.2.2. Dose Modifications for Hematologic and Non-hematologic Toxicities Related to Selinexor

The criteria for dose modification for toxicities at least possibly related to selinexor are outlined below in Table 1. Supportive care guidelines for management of selinexor-related toxicities and indications for dose modifications are described in Table 2.

Table 1. Pre-specified Dose Modifications for AEs Related to Study Drug

	Dose Level		
Starting Dose	1	60mg	twice weekly
Dose Reductions	-1	40 mg	twice weekly
	-2	40 mg	once weekly

Table 2. Supportive Care and Dose Modification Guidelines

Toxicity and Intensity	Supportive treatment	Selinexor Dose Modification
Fatigue (common)		
Grade 1	Rule out other causes of fatigue. Consider addition of 4-8 mg dexamethasone or equivalent on the day after selinexor. Insure adequate caloric intake and assess volume status.	Maintain dose.
Grade 2	Rule out other causes of fatigue. Consider addition of 4-8 mg dexamethasone or equivalent on the day after selinexor. Insure adequate caloric intake and assess volume status. For additional support see NCCN fatigue guidelines.	Maintain dose. Consult medical monitor for additional option such as temporarydose reduction or short dose interruptions.
Grade 3	See above guidelines for Grade 2 fatigue	Interrupt selinexor dosing until resolved to Grade ≤ 2, For first occurrence of Grade 3, if adequate supportive care resulted in fatigue improving to Grade ≤ 1 within 7 days, restart selinexor at current dose. Otherwise, restart selinexor one dose level lower
Anorexia or Weight loss		
Grade 1	Rule out other causes of anorexia. Assess dietaryoptions (e.g., try a variety of other foods). Add high-calorie supplements (e.g., Ensure®). Consider addition of 4-8 mg dexamethasone or equivalent on the day after selinexor dosing.	Maintain dose.
Grade 2	Rule out other causes of anorexia.  Assess dietaryoptions (e.g., try a variety of other foods).  Add high-calorie supplements (e.g., Ensure®).  Consider addition of 4-8 mg dexamethasone or equivalent on the day after selinexor.  Consider megesterol acetate 80-400 mg daily.  Consider anabolic steroids such as oxandrolone, or dronabinol (Marinol®) or other cannabinoid, mainlyfor patients who cannot tolerate steroids or are at high risk to progress.  For additional supportive care see NCCN guidelines (see Appendix 8).	Selinexor may be skipped intermittently while supportive medications are instituted, usuallyfor < 1 week.

Toxicity and Intensity	Supportive treatment	Selinexor Dose Modification
Grade 3	See guidelines for Grade 2 anorexia above	Interrupt dosing with selinexor.
		Restart selinexor at 1 dose level reduction
		(see Table 1) once anorexia resolves to Grade ≤ 2 and patient is clinicallystable.
Grade 4 (anorexia only)	See guidelines for Grade 2 anorexia above	Stop dosing of selinexor.
, ,,		Restart selinexor at 1 dose level reduction
		(see Table 1) only if anorexia resolves to
		Grade ≤ 2, patient is clinically stable other contributing factors have been addressed.
Nausea, Acute (common)		Contributing factors have been addressed.
Grade 1	Ensure adequate caloric intake and assess	Maintain dose.
	volume status.	
	Consider alternate 5-HT3 antagonists and/or D2 antagonists as needed. Consider addition of	
	NK1 antagonists.	
	Consider addition of 4-8 mg dexamethasone or	
0 1 0	equivalent on the day after selinexor.	
Grade 2	See guidelines for Grade 1 nausea above. For additional options see NCCN guidelines for	Selinexor may be skipped intermittently while supportive medications are instituted,
	antiemesis (see Appendix 7).	usuallyfor <1 week.
Grade 3	See guidelines for Grade 1 nausea.	Interrupt selinexor dosing until resolved to
	For additional options see NCCN guidelines for	Grade ≤ 2. For first occurrence of Grade 3,
	antiemesis (see Appendix 7).	if adequate supportive care resulted in nausea improve to Grade ≤ 1 within 3 days,
		restart selinexor at current dose.
		Otherwise, restart selinexor one dose level
		lower (see Table 1). If nausea stabilizes for
		at least 4 weeks at Grade ≤ 1, original dose of selinexor may be resumed.
Hyponatremia (common)		or commencer may be recumed.
Grade 1 (sodium levels <	Ensure that sodium level is corrected for	Maintain dose.
Normal to 130 nM)	hyperglycemia (serum glucose > 150 mmol/L).	
	Rule out other causes of low sodium (e.g., cardiac, hepatic, adrenal, renal and thyroid	
	diseases, SIADH, Fanconi Syndrome,	
	hyperglycemia, diuretic use).	
	Consider salt supplementation 1-2 times per	
Grade 3 (sodium levels	Ensure that sodium level is corrected for	Hold selinexor until Grade ≤ 1 (≥ 130 nM),
126-129 nM) without	hyperglycemia (serum glucose > 150 mmol/L).	restart on the same dose level.
Symptoms	Rule out other causes of low sodium (e.g.,	
	cardiac, hepatic, adrenal, renal and thyroid diseases, SIADH, Fanconi Syndrome,	
	hyperglycemia, diuretic use).	
	Initiate salt supplementation 2-3 times per day.	
Grade 3 (120-125 nM) or	Correct sodium as per institutional guideline	Hold selinexor until resolved to Grade ≤ 1
Grade 4 or Grade 3 with Symptoms	Initiate salt supplementation 2-3 times per day.	(≥ 130nM) then reduce selinexor dose by1
Cympionia		level (See Table 1). For Grade 3 hyponatremia, if serum sodium stabilizes to
Cymptoma		hyponatremia, if serum sodium stabilizes to grade ≤ 1 for at least 4 weeks, original dose
		hyponatremia, if serum sodium stabilizes to
Diarrhea (common)	Diet recommendation as ner guidalings	hyponatremia, if serum sodium stabilizes to grade ≤ 1 for at least 4 weeks, original dose of selinexor may be resumed.
	Diet recommendation as per guidelines	hyponatremia, if serum sodium stabilizes to grade ≤ 1 for at least 4 weeks, original dose of selinexor may be resumed.  For Grade 2 only, reduce selinexor one
Diarrhea (common)	Diet recommendation as per guidelines (Benson, 2004) b . Institute standard anti-diarrheal therapy.	hyponatremia, if serum sodium stabilizes to grade ≤ 1 for at least 4 weeks, original dose of selinexor may be resumed.
Diarrhea (common)	(Benson, 2004) b . Institute standard anti-diarrheal therapy. After the first occurrence of diarrhea,	hyponatremia, if serum sodium stabilizes to grade ≤ 1 for at least 4 weeks, original dose of selinexor may be resumed.  For Grade 2 only, reduce selinexor one dose level (See Table 1) until resolved to
Diarrhea (common)	(Benson, 2004) b . Institute standard anti-diarrheal therapy. After the first occurrence of diarrhea, Ioperamide 2 mg should be considered	hyponatremia, if serum sodium stabilizes to grade ≤ 1 for at least 4 weeks, original dose of selinexor may be resumed.  For Grade 2 only, reduce selinexor one dose level (See Table 1) until resolved to ≤ Grade 1, then re-start at the current dose
Diarrhea (common)	(Benson, 2004) b . Institute standard anti-diarrheal therapy. After the first occurrence of diarrhea,	hyponatremia, if serum sodium stabilizes to grade ≤ 1 for at least 4 weeks, original dose of selinexor may be resumed.  For Grade 2 only, reduce selinexor one dose level (See Table 1) until resolved to ≤ Grade 1, then re-start at the current dose

Toxicity and Intensity	Supportive treatment	Selinexor Dose Modification
Grade 3	Institute IV fluids.  Diet recommendation as per guidelines (Benson 2004) b .  Institute standard anti-diarrheal therapy.  Once the symptoms resolve to ≤ Grade 1,  Ioperamide 2 mg should be considered prophylacticallyapproximately1-2 hours before the administration of selinexor and repeated every 4 hours for the first 12 hours.	Delay selinexor until resolved to ≤ Grade 1, then reduce selinexor dose by one dose level (See Table 1). If diarrhea stabilizes for at least 4 weeks at Grade ≤ 1, then original dose of selinexor maybe resumed.
Grade 4	Rule out other causes of diarrhea, including infectious agents. In case of opportunistic infection, withdraw all steroids (with tapering if medicallyappropriate) until culture is negative. Follow institutional guidelines for Grade 4 diarrhea.	Delay selinexor until resolved to ≤ Grade 1, then reduce selinexor dose by one dose level (See Table 1)
Thrombocytopenia c	l N	
Grade 1	None	Maintain dose.
Grade 2	Consider implementing platelet growth factors (eltrombopag or romiplostim +/- oprelvekin [IL-11]) and platelet transfusions, per institutional guidelines.  Monitor platelet counts weekly.	
Grade 3 Thrombocytopenia Without bleeding	Initiate platelet growth factors (eltrombopag or romiplostim +/- oprelvekin [IL-11]) and platelet transfusions per institutional guidelines.  Monitor platelet counts at least weekly.	In general selinexor dose should be reduced one dose level (see See Table 1). In certain cases when there is significant disease involvement in the bone marrow (e.g., in heavily pretreated multiple myeloma) or pre-existing compromised marrow function (e.g., due to prior marrow-toxic therapy), the Investigator in consultation with the Sponsor maydecide to continue Selinexor dosing, provided that platelet counts and bleeding symptoms/signs are closelymonitored.
Grade 4 Thrombocytopenia Without bleeding	Follow guidelines (above) for Grade 3 thrombocytopenia without bleeding. Transfuse as per institutional guidelines.	In general, hold selinexor dos until platelet counts >50,000/mm³ or baseline, then resume selinexor dosing at one dose level lower (See Table 1). In certain cases when there is significant disease involvement in the bone marrow (e.g., in heavily pretreated multiple myeloma) or pre-existing compromised marrow function (e.g., due to prior marrow-toxic therapy), the Investigator in consultation with the Sponsor may decide to continue Selinexor dosing, provided that platelet counts and bleeding symptoms/signs are closelymonitored.
≥ Grade 3 Thrombocytopenia with bleeding	Transfuse as per institutional guidelines. Follow guidelines for Grade 3 thrombocytopenia without bleeding.	Hold selinexor dosing until platelet counts >50,000/ mm  or baseline, then resume selinexor dosing at one dose level below (See Table 1)
Neutropenia		
Grade 3 Neutropenia without fever	Implement growth factors per institutional guidelines until neutrophils are consistently > 1,500/mm  .	Maintain dose.

Toxicity and Intensity	Supportive treatment	Selinexor Dose Modification
Grade 4 Neutropenia without fever	Implement growth factors per institutional guidelines.	Reduce selinexor dose byone level (See Table 1).  After implementation of growth factors, for patients who achieve neutrophil levels > 1,500/mm³ for > 4 weeks (in the presence or absence of growth factors), selinexor dose maybe re-escalated, with frequent monitoring implemented.
Grade 3 or 4 Neutropenia with fever (febrile neutropenia)	Implement growth factors per institutional guidelines. Implement broad anti-microbial coverage per institutional guidelines. Please note that selinexor has not been associated to date with any opportunistic infections	Hold selinexor until fever resolves and patient is clinicallystable. When patient is clinically stable, restart dosing one dose level lower (See Table 1) After implementation of growth factors, for patients who achieve neutrophil levels >1,500/mm³for >4 weeks, selinexor dose may be re-escalated, provided frequent monitoring is implemented.
Other Selinexor-related A	dverse Events d	
Grade 1 or 2	Initiate standard supportive care per institutional guidelines.	Maintain dose.
Grade 3	Initiate standard supportive care and follow institutional guidelines.	Delay dose until resolved to Grade ≤ 1 or baseline, then reduce by one dose level (See Table 1)
Grade 4	Initiate standard supportive care and follow institutional guidelines.	Delay dose until resolved to Grade ≤ 1 or baseline, then reduce by two dose levels (See Table 1)

All dose modifications should be based on the worst preceding toxicity.

<sup>a National Comprehensive Cancer Network®. NCCN Clinical Practice Guidelines in Oncology(NCCN Guidelines®): Fatigue. Available at http://www.nccn.org/professionals/physician\_gls/pdf/fatigue.pdf

<sup>b Benson AB, Ajani JA, Catalano RB, et al. Recommended guidelines for the treatment of cancer treatment-induced diarrhea. J Clin Onc 2004; 22:2918.

 $^{\rm c}$  Isolated values of  $\geq$  Grade 3 alkaline phosphatase values will NOT require dose interruption. Determination of liver vs. bone etiology should be made, and evaluation of gamma-glutamyl transferase (GGT), 5'-nucleotidase (5'NT), or other liver enzymes should be performed.

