- 3. Patients with Myelodysplastic Syndromes refractory (primary or acquired resistance) to hypomethylating agents(decitabine or 5-azacytidine). At least 4 1month cycles of prior decitabine or SGI-110 OR 6 1month cycles of 5-azacytidine (IV, subcutaneous, or oral is required unless the patient has progressive disease prior to completing the required number of cycles.
- Histologically confirmed diagnosis of a Myelodysplastic Syndrome, meeting criteria for any subtype in the FAB or WHO classification systems with any IPSS score.
- 5. Patients with MDS who relapse after allogeneic stem cell transplant are eligible if they received standard dose decitabine or 5-azacytidine prior to or after stem cell transplant as defined in inclusion criteria 3.
- 6. If patient has undergone prior allogeneic stem cell transplant, they must be greater than 100 days post transplant and have ≤ grade 2 graft-versus-host disease
- 7. There is no upper limit on the number of prior treatments provided all inclusion/exclusion criteria are met
- 8. Eastern Cooperative Oncology Group (ECOG) Performance Status of 0-2 (Appendix 1).
- 9. Patients receiving erythropoietin (darbepoetin, epoetin alfa) must be on a stable dose and with stable transfusion requirement or hemoglobin level during the 8 weeks prior to study entry.
- Adequate hepatic function within 21 days prior to C1D1: total bilirubin <2 times the upper limit of normal (ULN), asparate aminotransferase (AST) <2.5 times ULN and alanine aminotransferase (ALT) <2.5 times ULN.
- 11. Adequate renal function within 21 days prior to C1D1: estimated creatinine clearance of ≥ 30 mL/min, calculated using the formula of Cockroft and Gault (140-Age) Mass (kg)/(72 creatinine mg/dL); multiply by 0.85 if female.
- 12. Female patients of child-bearing potential must agree to use dual methods of contraception and have a negative serum pregnancy test at screening, and male patients must use an effective barrier method of contraception if sexually active with a female of child-bearing potential. Acceptable methods of contraception are condoms with contraceptive foam, oral, implantable or injectable contraceptives, contraceptive patch, intrauterine device, diaphragm with spermicidal gel, or a sexual partner who is

Memorial Sloan Kettering Cancer Center

IRB Number: 14-005 A(17) Approval date: 25-Jan-2021

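### Two hyponatremia rows of the dosing table set the glucose trigger for correcting sodium at 150 mmol/L (about 2,700 mg/dL), evidently a unit slip for mg/dL

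*Combined protocol and SAP*

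**What the plan says.** Table 2 (Section 9.2.2) has three hyponatremia rows.

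- **Grade 1** (sodium from below normal down to 130). The supportive-care column begins "Ensure that sodium level is corrected for" and continues "hyperglycemia (serum glucose > 150 mmol/L"). It then lists other causes to exclude, hyperglycemia among them with no figure attached. Salt supplements are optional, and the dose is maintained.
- **Grade 3 without symptoms** (126-129). The correction instruction, the glucose figure and the list of causes are the same. Salt supplements are to be started. Selinexor is held until sodium is back to Grade 1 or better, and the patient is then to "restart on the same dose level".
- **Grade 3 at 120-125, Grade 3 with symptoms, or Grade 4.** The instruction is "Correct sodium as per institutional guideline", with no glucose figure. This is the only row that reduces the dose.

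Section 9.2.5 lists exceptions for which selinexor need not be held. One is "Electrolytes abnormalities that are reversible with oral supplements or brief intravenous infusions".

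**The concern.** The figure is a decision threshold in a table that governs dosing, and it cannot work as printed. High glucose lowers measured sodium, so correcting first is meant to stop a glucose effect being graded as a drug toxicity. If the correction is reserved for glucose above 150 mmol/L, it is never made.

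At stake is the choice between two adjacent rows. A measured sodium of 126-129 that corrects to 130 or above belongs in the Grade 1 row, where the dose is maintained. Left uncorrected, it falls in the asymptomatic Grade 3 row, where selinexor is held and salt is started.

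The situation is not remote. Section 11 lists low sodium among effects seen in more than 20 of 100 people, and the KCP-330-002 toxicity table in Section 3.2 shows Grade 3 hyponatremia in 8 patients (16%). Neither source says how often glucose contributed.

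**Working it through.** **Inputs**
- Printed trigger: 150 mmol/L, in two rows of Table 2, Section 9.2.2.
- Row boundaries: Grade 1 down to 130, asymptomatic Grade 3 at 126-129 (same table).
- Molar mass of glucose: 180.156 g/mol. This is a physical constant, not in the documents. It gives 1 mmol/L = 180.156 / 10 = 18.016 mg/dL.
- Sodium correction: 1.6 to 2.4 mmol/L for each 100 mg/dL of glucose above 100. This is an assumption, not in the documents, and is used only to judge plausibility.

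**Step 1: convert the printed trigger.** 150 × 18.016 = 2,702 mg/dL.

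**Step 2: convert the presumed intent.** 150 mg/dL / 18.016 = 8.33 mmol/L. The ratio of printed to intended is 150 / 8.33 = 18.0, which is simply the unit conversion factor.

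**Step 3: is the printed trigger plausible?** The correction is factor × (glucose − 100) / 100.

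| Glucose (mg/dL) | Correction at 1.6 (mmol/L) | Correction at 2.4 (mmol/L) |
|---|---|---|
| 150 | 0.8 | 1.2 |
| 300 | 3.2 | 4.8 |
| 500 | 6.4 | 9.6 |
| 2,702 | 41.6 | 62.5 |

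A rule that starts correcting only when the adjustment is already about 42 to 62 mmol/L makes no sense beside a row that is 126-129 wide.

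**Step 4: what glucose would move a patient from the hold row to the maintain row?** Solve glucose = 100 + 100 × (rise needed) / factor.
- From 129 to 130 (rise of 1): 100 + 100/2.4 = 142 mg/dL, to 100 + 100/1.6 = 163 mg/dL.
- From 126 to 130 (rise of 4): 100 + 400/2.4 = 267 mg/dL, to 100 + 400/1.6 = 350 mg/dL.

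The glucose values that matter therefore run from about 142 to 350 mg/dL. The highest is 350 / 18.016 = 19.4 mmol/L, roughly an eighth of the printed trigger. A trigger of 150 mg/dL sits at the lower end of this range, where a screening threshold belongs.

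**Step 5: count the affected rows.** The trigger is in 2 of the 3 hyponatremia rows. It can change the dosing action in 1 of them, because the Grade 1 row maintains the dose either way.

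**Step 6: look for a correction elsewhere.** No other section restates the glucose threshold. The synopsis gives another serum analyte in conventional units ("creatinine mg/dL", in the renal-function criterion), which supports mg/dL as the intended unit here.

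**The case against.** The best reply is that nobody would apply the number. A physician would see that 150 mmol/L is a misprint, and the unnumbered instruction to exclude hyperglycemia covers the case anyway.

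There are further safeguards. Section 9.2.7 requires consultation with the Principal Investigator on every delay or modification. The notes to the Section 10.0 calendar require investigator review of chemistry before all cycle 1 dosing, and the panel reports sodium and glucose together. Section 9.2.5 relaxes holds for some electrolyte abnormalities. The study is single-center, so sites cannot read the table differently. Finally, no passage states the threshold in mg/dL, so the intended unit is inferred.

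Most of this stands as a limit on harm, but none of it repairs the figure. The Section 9.2.5 exception concerns abnormalities that respond to supplements or brief infusions, which does not clearly describe low sodium caused by high glucose.

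It could also be said that glucose-related low sodium is not related to selinexor and so falls outside Table 2. That does not remove the hold: Section 9.2.1 also holds the drug for an unrelated non-hematologic event of Grade 3 or higher and restarts at the same dose. The uncorrected grade is what triggers the hold under either section.

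**Conclusion.** The threshold is wrong as printed in both rows, by a factor of about 18 (150 against 8.3 mmol/L; 2,702 against 150 mg/dL). The practical effect is small: one row, a temporary hold, a restart at the same dose, and several safeguards around it. The documents give no count of patients with glucose-related sodium of 126-129, so none is claimed. The primary endpoint, sample size and error rates are untouched.

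That the printed value is unusable follows from the unit conversion. That mg/dL was meant is a strong inference: 150 is a sensible cut-off in that unit and an impossible one in mmol/L. The correction factors used in the plausibility check are assumed, and the conclusion is the same across their range.

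**What to change.** In the Grade 1 and asymptomatic Grade 3 (126-129) rows of Table 2, change the trigger to **> 150 mg/dL (8.3 mmol/L)**, after the clinical team confirms that unit. Giving both units prevents the slip from recurring.

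While editing, check in the source file that the sodium limits in these rows read mmol/L. The text available for this review shows nM (for example "Normal to 130 nM"), which may come from the PDF conversion and is not counted as an error.

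The cost is one unit changed in two rows of one table, with no effect on design, sample size or analysis.
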